5. ANALYSIS POPULATIONS

The study will use following analyses population for data summarization.

Table 16: Analysis Population

Population	Definition	Displays
Day-180 Observational Population	The Day-180 Observational Population includes all rollover subjects from studies EN3835-302/303.	The protocol deviations, demographic characteristics and safety analysis for the data obtained from Screening to Day 180 will be based on this population. The reduction of response, complete loss of response, and all cellulite assessments (ie, changes in CR-/PR-PCSS, PR-CIS, S-GAIS, SSRS, and subject satisfaction with cellulite treatment at Day 180 will be summarized.
Prior to Day 180 Population	Prior to Day 180 Population includes all subjects who did not meet inclusion criteria #2 or inclusion criteria #5 or those who withdrew from the study due to SAE/AE, or lost to follow-up prior to Day 180.	The protocol deviations, demographic characteristics and safety analysis for the data obtained from Screening to Day 180 will be based on this population.
Open Label Observation Population	The Open Label Observation Population includes all subjects who enter the open-label study and received active CCH in EN3835-302 or EN3835-303. This population will include all Category I, II, and III subjects including the subjects who received retreatment in the Open-label Period.	The protocol deviations, demographic characteristics and safety parameters for the open label period prior to retreatment will be summarized based on this population.
Time to Reduction of Response (TRR) Population Before Retreatment	The TRR Population Before Retreatment includes all subjects who have at least a 1-level or 2-level improvement in both CR-PCSS and PR-PCSS ratings during the double-blind study for either/both treated buttocks. This population will include Category I and II subjects. Reduction of response will be evaluated separately for subjects who have at least a 1-level and 2-level improvement in both CR-PCSS and PR-PCSS ratings during the double-blind study in each treated buttock. The reduction of response prior to retreatment will be analyzed using this population.	The analyses of cellulite assessments prior to retreatment, and demographic characteristics will be based on this population.

Table 16: Analysis Population (Continued)

Population	Definition	Displays
Open Label Retreated (OLR) Population	The OLR Population includes all subjects in TRR population who are retreated in the open label period of this study.	The analyses of cellulite assessments after retreatment ie, improvement of response during retreatment phase (Day 1 to Day 71+5 days of retreatment), study drug exposure during retreatment, Safety assessments after retreatment will be based on this population.
Open Label Not Retreated (OLNR) Population	The Open Label Not Retreated Population includes all subjects in TRR Population who are NOT retreated in the open label period of study.	All analyses for change from baseline in Day 1, or Day 71, and responder analysis based on this population will be performed
Time to Reduction of Response (TRR) Population After Retreatment	The TRR Population After Retreatment includes all subjects in OLR Population who have at least 1 level or 2-level improvement in both CR-PCSS and PR-PCSS ratings at Day 71/End of Treatment Session in the open label retreatment period. Reduction of response will be evaluated separately for subjects who have at least a 1-level and 2 level improvement in both CR-PCSS and PR-PCSS ratings during the open label treatment period in each treated buttock. The reduction of response after retreatment will be analyzed using this population.	The reduction of response in open label retreatment period compared to the score at Day 71 of retreatment period will be based on this population.

6. STATISTICAL METHODS

6.1. General Methodology

All summary tables and data listings will be prepared using version 9.4 or later of statistical analysis software (SAS®) software.

Continuous data will be summarized using descriptive statistics (number of subjects [n], mean, standard deviation [SD]/ or standard error [SE], median, minimum [min], and maximum [max]) and discrete data will be summarized using frequency counts and percentages, the denominator will be based on the number of subjects in the appropriate population. For the purpose of display, the summary results will be rounded as follows:

- Min and max: same number of decimal places as the raw data.
- Mean and median: one more decimal place than the raw data.
- SD/SE: two more decimal places than the raw data.
- Percentages will be displayed with one decimal precision. A zero count will not have the associated percentage presented on the table (ie, no 0%).
- The standard form of a percentage change variable is 0 decimal places.

For categorical variables with missing values, a category documenting the frequency of missing values will be displayed in the summary tables.

Summary tables, subject listings, graphs and any supportive SAS output will include a “footer” of explanatory notes that will indicate, when applicable:

- Date of data extraction
- Date and time of output generation
- SAS program name, including the path, that generates the output

When calculating percentages, the denominator will be based on the number of subjects with non-missing values. If the denominator is expected to change over time, then the denominator used to calculate the percentage should be based on the number of subjects with non-missing values at each visit. Any subject removed from an analysis will be noted at the bottom of the table along with the reason the subject was removed.

Null summary tables will be presented with a note stating that “No Subjects Met Criteria.” Subject listings of all data from the CRFs as well as any derived variables will be presented.

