6.3. Handling of Missing Data

Subjects who discontinue the study prior to or after the initiation of the study drug will not be replaced and available data of these subjects until the point of discontinuation will be summarized. The missing baseline assessment will not be imputed.

For categorical variables with missing values, a category documenting the frequency of missing values will be displayed in the summary tables.

Subjects who discontinue early will be requested to complete all EOS procedures and assessments at an early termination visit.

There will be no imputation of missing values for safety data, however missing relationship between AE and study drug will be considered as related to study drug following worst case principle. Missing severity of an AE will be summarized as a severe AE.

Immunogenicity samples with a positive titer value will undergo a log transformation for analyses. Samples with titer level less than 1 will be assigned or imputed as a log transformed titer of zero (0) for analyses.

PR-CIS total score when scores are missing

If scores on at least two of the 6 items are missing, then PR-CIS total score will be calibrated to 6 and computed as:

- Total PR-CIS Score = (Sum of the Scores ÷ Number of question answered) x 6

If scores on three or more of the six items are missing, then the PR-CIS total score will be set to missing.

PR-CIS abbreviated total score when scores are missing

If scores on at least of the 5 items are missing, the PR-CIS abbreviated total score will be computed as:

- Abbreviated total PR-CIS Score = (Sum of the Scores ÷ Number of question answered) x 5

If scores on three or more of the five items are missing, then the PR-CIS abbreviated total score will be set to missing.

Composite response when PR-PCSS and/or CR-PCSS component missing

If the classification is missing for 1 or both components (ie, the PR-PCSS component or the CR-PCSS component), then the composite responder classification is missing for that visit.

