7.6.2. Reduction of response using PR-PCSS and CR-PCSS Prior to Retreatment

The proportion of subjects or buttocks with reduction of response (refer to section 4.4.1) will be summarized using frequency counts and percentages using TRR Population Before Retreatment and OLNLR Population subject category (ie, Category I and II, and Overall) and treatment area (ie, left and/or buttock) at the following visits prior to retreatment: Day 180, Month 12, 18, 24, and 36 where reduction of response is assessed.

The proportions will be computed based upon number of subjects within each category and treatment area remains not-retreated prior to that visit.

The following efficacy end points for reduction of response will be summarized:

- Proportion of subjects with 2-level composite reduction
- Proportion of subjects with 1-level composite reduction
- Proportion of subjects with complete loss of response

The time to composite reduction of response (ie, by 1-level and 2-level separately) and time to complete loss of response (refer to section 4.4.1 for derivation) will be summarized descriptively using TRR Population Before Retreatment and OLNLR Population.

The listings of cellulite PR-PCSS and CR-PCSS severity ratings will be provided for All Subjects prior to retreatment.

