7.6.3. Reduction of response using PR-PCSS and CR-PCSS after Retreatment

The proportion of subjects with reduction of response (refer to section 4.4.1) will be summarized using frequency counts and percentages using TRR Population after Retreatment by subject category (ie, Category I and II, and Overall) and treatment area (ie, left and/or buttock) at all observation visits after retreatment where cellulite assessments has been performed.

The proportions will be computed based upon number of subjects within each category and treatment area retreated prior to that visit.

The following efficacy end points for reduction of response will be summarized:

- Proportion of subjects with 2-level composite reduction
- Proportion of subjects with 1-level composite reduction
- Proportion of subjects with 2-level reduction on either scale
- Proportion of subjects with 1-level reduction on either scale
- Proportion of subjects with complete loss of response

The time to composite reduction of response (ie, by 1-level and 2-level separately), time to partial response and time to complete loss of response (refer to section 4.4.1 for derivation) will be summarized descriptively using TRR Population after Retreatment.

The listings of cellulite PR-PCSS and CR-PCSS severity ratings will be provided for subjects in OLR Population after Retreatment.

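### The SAP gives conflicting percentage denominators, and the loss-of-response rules in 7.6.2 and 7.6.3, applied literally, keep unrated subjects in the denominator

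*SAP*

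**What the plan says.** Section 6.1 (General Methodology) contains two general rules. For discrete data, "the denominator will be based on the number of subjects in the appropriate population". Further down, "When calculating percentages, the denominator will be based on the number of subjects with non-missing values", and where the denominator is expected to change over time, "the denominator used to calculate the percentage should be based on the number of subjects with non-missing values at each visit". Section 6.1 also requires this: "For categorical variables with missing values, a category documenting the frequency of missing values will be displayed in the summary tables".

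The loss-of-response sections have rules of their own. Section 7.6.2, before retreatment: "The proportions will be computed based upon number of subjects within each category and treatment area remains not-retreated prior to that visit". Section 7.6.3, after retreatment: "The proportions will be computed based upon number of subjects within each category and treatment area retreated prior to that visit". Section 7.6.3 tabulates these proportions "at all observation visits after retreatment where cellulite assessments has been performed".

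Section 6.3 covers a visit at which the PR-PCSS or CR-PCSS component, or both, is missing: "then the composite responder classification is missing for that visit". Section 4.4.2 (Table 13) says the same.

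**The concern.** The two general rules in 6.1 give different percentages as soon as any value is missing. The rules in 7.6.2 and 7.6.3 differ from both, because they select subjects by retreatment status alone. The SAP does not rank these rules, so two programmers could report different loss-of-response percentages from the same data.

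The direction of the difference matters. A subject with no composite classification at a visit cannot be counted as having lost response. If she stays in the denominator, she lowers the percentage exactly as a subject with maintained response would. Follow-up runs to Day 1080, and Section 7.1 plans to tabulate discontinuations in every interval to Month 36. Unrated subjects should therefore accumulate at later visits, where durability is judged, and the response would look more durable than the rated subjects show.

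**Working it through.** The SAP states no figure for this point, so there is nothing to reproduce. The check compares the rules and then does the arithmetic.

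**Who is in the denominator at a visit before retreatment?**

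- Rule A (6.1, population count): everyone in the analysis population.
- Rule B (6.1, non-missing values by visit): only subjects with a value at the visit.
- Rule C (7.6.2): everyone not yet retreated before the visit, rated or not.

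Section 7.6.3 is the counterpart of rule C after retreatment: everyone retreated before the visit, rated or not.

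**Who can be in the numerator?** Only subjects with both ratings, because the composite classification is otherwise missing (4.4.2, 6.3). Complete loss of response is also defined on both scales. The numerator is read as loss observed at the visit, since both sections tabulate by visit.

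**The plainest case.** Section 7.6.2 also applies its rule to the Open Label Not Retreated Population. Table 16 defines this as subjects never retreated in the open-label period. All of them are still not retreated at every visit. Read literally, the denominator in each category and treatment area therefore stays fixed from Day 180 to Month 36, including subjects who have left the study.

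**Formulas.** Let p be the loss proportion among rated subjects, m the share of the at-risk set with no composite rating, R the at-risk number and N the population number.

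- Rule B: p
- Rule C: p × (1 − m)
- Rule A: p × (1 − m) × R / N

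**Illustration before retreatment.** All inputs are assumed: N = 200, 60 retreated earlier, so R = 200 − 60 = 140, and p = 40%.

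| m | Rated, 140 × (1 − m) | Losses, 0.40 × rated | Rule B, losses / rated | Rule C, losses / 140 | Rule A, losses / 200 |
|---|---|---|---|---|---|
| 0% | 140 | 56.0 | 40.0% | 40.0% | 28.0% |
| 10% | 126 | 50.4 | 40.0% | 36.0% | 25.2% |
| 20% | 112 | 44.8 | 40.0% | 32.0% | 22.4% |
| 30% | 98 | 39.2 | 40.0% | 28.0% | 19.6% |
| 40% | 84 | 33.6 | 40.0% | 24.0% | 16.8% |

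Rules B and C agree only when nobody is unrated. Rule A also falls with the number already retreated, so it differs from the other two even at m = 0. The relative understatement under rule C equals m whatever p is: at m = 20%, a p of 20% becomes 16% and a p of 60% becomes 48%.

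**The case against.** The best reply is that the rules stack and need not compete. On that reading, 7.6.2 and 7.6.3 say who is eligible at a visit, and the by-visit sentence in 6.1 then removes missing ratings. The eligible sets do change over time, which is the condition that sentence names. The result would be the denominator recommended here. This is a reasonable reading, but the SAP does not state it, and a rule written for a specific analysis is commonly taken to replace the general one. The conflict between the two general rules in 6.1 remains in any case.

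Four further replies stand in whole or in part.

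- A reader might infer that the plan treats a missing rating as no loss. It does not say so: it calls the classification missing and asks for a missing category. The understatement is an arithmetic effect of the literal denominator. A missing row would disclose the problem but not correct the percentage.
- A reader might add visits skipped because of retreatment as a built-in source of missing ratings. That largely fails. In the example in Section 3.1.2, retreatment starts on Day 351 and Day 360 is skipped. By Day 360 that subject has left the 7.6.2 set. Her course runs to Day 421, so she has not yet reached the observation phase after retreatment that 7.6.3 describes. Dropout, missed visits and missing components remain as sources.
- The rated-only figure need not be the truth. If dropout depends on response, it is biased too.
- The table layouts are in SAP Module 2, which is not at hand and may state denominators table by table. The text of the SAP should still not contradict itself.

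**Conclusion.** The conflict is real and should be resolved in the text. Section 6.1 states two denominators that cannot both hold when data are missing. Sections 7.6.2 and 7.6.3 add at-risk denominators with no condition on having a rating, and nothing says which governs. Taken literally, those two sections scale the loss proportion by (1 − missing share), always towards apparent durability.

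The actual size is unknown, because the SAP gives neither an expected loss nor an expected missing share. The fall from 40% to between 36% and 24% rests entirely on assumed missing shares of 10% to 40%.

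A reader might conclude that the secondary objective itself is biased. The documents do not support that. Section 2.2 names time to reduction of response, which Table 17 derives from visit dates and 7.6.2 and 7.6.3 summarise descriptively. The denominators at issue do not enter those summaries. They affect the visit-wise proportions reported beside them. Nor is the plan shown to produce biased results, since the stacked reading would avoid the problem.

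**What to change.** - In 6.1, limit the population-count sentence to tables such as adverse events and demographics. Say that the missing category is shown as a count outside the percentage base wherever the non-missing rule applies.
- In 7.6.2, define the denominator at each visit as subjects, per treatment area, not retreated before that visit and with both PR-PCSS and CR-PCSS ratings at that visit.
- In 7.6.3, use the same definition for subjects already retreated. State separately which rating or ratings the either-scale proportions require.
- Print the at-risk number and the number without a rating beside each percentage.

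The cost is SAP wording and two extra counts per cell; no new data are needed. Late loss-of-response percentages will look less favourable than under the literal rule. The rated-only figure still assumes that unrated subjects resemble rated ones, which is why the missing count must appear with it.

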6.2. Derived Variables

Refer to Table 17 below for the listing of the derived variables and their definitions for study parameters.

Table 17: Derived Variables and Definition

Variable	Definition
Height (cm)	If height is recorded in inches, then height is equal to the recorded value multiplied by 2.54 and then rounded to 1 decimal point.
Weight (kg)	If weight is recorded in pounds, then weight is equal to the recorded value multiplied by 0.454 and then rounded to 1 decimal point.
Body Mass Index (BMI)	BMI will be computed using height and body weight measured at screening as, $BMI (kg/m^2) = Weight (kg) / Height (m)^2$
Relative Day 1 (retreatment phase)	The date of first injection of study drug during Open-label Period will be considered as relative Day 1 for Category I and II retreated subjects who took retreatment during current study.
Study Day (retreatment phase - for assessment on or after the Day 1)	Study Day will be computed as, Date of Assessment – Date of relative day 1 + 1
Study Day (retreatment phase - for assessment before Day 1)	Study Day will be computed as, Date of Assessment – Date of relative day 1
Relative Day 1 (overall study)	The date of Screening Visit (within 14 days after Day 71/EOS of double-blind study) in this study will be considered as relative Day 1
Study Day (overall study- for assessment on or after the Day 1)	Study Day will be computed as, Date of Assessment – Date of relative day 1 + 1
Baseline for Safety Parameters after Retreatment	For visits prior to/on first day of retreatment, Baseline is defined as the assessment values at Day 71/EOS visit in double-blind studies (EN3835-302/303). For visits after first day of retreatment, baseline is defined as the last non-missing measurement/assessment prior to/on the first dose date of retreatment. For vital signs, the baseline will be the Day 1 pre-dose values. For clinical laboratories this could be the screening value, or it could be an unscheduled lab, if the unscheduled lab is the closest value preceding the first injection.

Table 17: Derived Variables and Definition (Continued)

Variable	Definition
Baseline for Safety parameters Before Retreatment	The measurements/assessment performed during Screening Visit of this study (within 14 days after/or Day 71/EOS Visit of double-blind period) will be considered as Baseline.
Baseline for Reduction of response and Improvement in Cellulite Severity (CR-PCSS and PR-PCSS)	
Improvement in Cellulite Severity: The assessment performed at Day 1 during the retreatment phase will be used as baseline to evaluate improvement in cellulite severity at Day 71 in this study.
 
Reduction of Response Prior to Retreatment: The assessment performed at Day 71/EOS visit in the double-blind phase will be used as baseline to evaluate reduction of response for any visits prior to/on first dose date of retreatment in this study.
 
Reduction of Response After Retreatment: The assessment performed at Day 71/End of treatment Session in the retreatment phase will be used as baseline to evaluate reduction of response during the observation phase after retreatment.

Baseline for CR-PCSS, PR-PCSS and PR-CIS Score	
At 180 Day Evaluation: The Screening assessment done within 14 days of Day 71/EOS of double-blind period will be used as baseline for 180 Day Evaluation period.
 
Before Retreatment: The Screening assessment done within 14 days of Day 71/EOS of double-blind period will be used as baseline for open-label period for subjects in TRR population who are not retreated, and until the point prior to retreatment for the subjects who are retreated.
 
After Retreatment: The assessments at Screening B/unscheduled assessment or Day 1 of the retreatment phase prior to/on the first dose date of retreatment in this study will be used as baseline.

Baseline for S-GAIS and Subject Satisfaction with Cellulite Treatment	The pretreatment Day 1 digital images from the double-blind study (EN3835-302/303) will be used as baseline.
Change from Baseline	Change from baseline will be derived as, post-baseline visit/time point value – the baseline value.
Time to reduction of response prior to retreatment (duration in days)	Date of visit where reduction is detected first – Date of Day 71/EOS of double-blinded studies 302/303
Time to reduction of response after retreatment (duration in days)	Date of visit where reduction is detected first – Date of Day 71/End of Treatment Session of open-label retreatment phase
Time to Complete Loss of Response prior to retreatment (duration in days)	Date of visit where complete loss of response reduction is detected first – Date of Day 71 of double-blinded studies 302/303 OR Date of Day 71/End of Treatment Session of open-label retreatment phase
Time to Complete Loss of Response after retreatment (duration in days)	Date of visit where complete loss of response reduction is detected first – Date of Day 71/End of Treatment Session of open-label retreatment phase
Last Date in Study	End date of last visit where subject was seen by investigator. If subject was lost to follow-up, then last date of contact. If the subject had contact with the site after the final visit (eg, to follow-up on an AE), the last visit date will still be used as last date in the study.

Table 17: Derived Variables and Definition (Continued)

Variable	Definition
Time in Study	Last date in study – Date of Screening visit (relative day 1 overall study) + 1
Duration of AE	AE end date – AE start date + 1
AE Onset Day (retreatment phase)	AE start date - Date of first injection + 1
AE Onset Day (overall study)	AE start date - Date of Screening Visit (relative day 1 overall study) + 1

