- ^l Assignment of subjects to Categories will occur after unblinding of investigators, subject and site personnel to subjects' treatment in EN3835-302/303 and will depend on treatment and Day 71 cellulite severity improvements. Depending on the date of the database lock of the double-blind studies, assignments may occur at Day 180 Visit after assessments are completed or at a time thereafter during an unscheduled visit.
- ^m Local adverse events associated with the injection site, including acute (eg, erythema, bruising, pain, nodules/mass, ulceration, blistering, pruritus, swelling, and/or induration) and/or chronic (eg, skin thickening, fibrosclerosis, peau d'orange changes) cutaneous adverse events, will be recorded and evaluated for seriousness and severity.
- ⁿ Any AE that occurs between the completion of studies EN3835-302/303 and the Day 180 Visit will be reported and evaluated.
EFP=Edematous fibrosclerotic panniculopathy; EOS=End of study; M=Month(s).

The Schedule of Events beyond Day 180 for Category I and II and who are eligible and opted to receive retreatment is provided in [Table 2](#).

Table 2: Schedule of Events: Eligible Category I/II Subjects – Treatment Session Assessments

Procedures^a	Screening B^b (Day -14 to -1 relative to Tx Visit 1)	Tx Visit 1 Tx Session 1 Day 1	Tx Visit 2 Tx Session 2 Day 22 (±3 days)	Tx Visit 3 Tx Session 3 Day 43 (±3 days)	Tx Visit 4 End of Treatment Day 71 (+5 days)^c
Informed consent ^d	X				
Inclusion/exclusion	X				
Digital photography ^e	X	X ^f	X ^f	X ^f	X
Prior/concomitant medications/procedures ^g	X	X	X	X	X
Physical examination:	X				
• Body weight	X		X ^h	X ^h	X
• Height	X				
Vital signs	X	X ⁱ	X ⁱ	X ⁱ	X
ECG ^j	X				
Collection of Samples					
• Clinical laboratory	X				X
• Anti-AUX-I/anti-AUX-II antibody level	X		X	X	X
• Pregnancy testing ^k	X	X ^h	X ^h	X ^h	X
Subject Cellulite Assessments					
• Review assessments' training and use materials	X	X	X	X	X
• Patient Reported Photonumeric Cellulite Severity Scale (PR-PCSS) ^{l,m}	X	X	X	X	X
• Subject Global Aesthetic Improvement Scale (S-GAIS) ^l	X				X
• Patient Reported Cellulite Impact Scale (PR-CIS) ^l	X				X
• Subject Satisfaction With Cellulite Treatment Assessment ^l	X				X
• Subject Self-Rating Scale (SSRS) ^l	X				X
Investigator Cellulite Assessments					
• Review assessment's training and use materials	X	X	X	X	X
• Clinician Reported Photonumeric Cellulite Severity Scale (CR-PCSS)	X	X	X	X	X
Selection of dimples to be treated		X	X	X	

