3.11.3. Vital Signs

Vital signs measurements include: systolic and diastolic blood pressure, respiratory rate, pulse rate, body temperature, height, and body weight.

Vital signs measurements (except height and body weight) will be taken at Screening (Day 71 of double-blind study), Day 180, and during Retreatment Phase [Screening B, Day 1, 22, 43, and 71 (End of Treatment/Early Termination)]. On the day of treatment (Day 1, 22, and 43), vital signs (except body temperature) will be measured up to 4 hours prior to study drug administration and at 15 and 30 minutes after the last injection; body temperature will be measured at 4 hours prior to study drug administration and at 30 minutes after the last injection.

Height and body weight measurements will be taken at Screening (Day 71 of double-blind study) for all subjects. Additionally, body weight will be measured at Day 180 and during treatment visits [Day 22, 43 and 71 (End of Treatment/Early Termination)] before injection.

Any abnormality in vital sign observed, will be considered as an AE or SAE as appropriate.

3.11.4. 12-Lead Electrocardiogram (ECG)

A 12-Lead ECG will be performed during the Screening B Visit if Screening B is performed greater than 12 months of an ECG obtained during the double-blind study. During the ECG measurement, the subject will be in a resting position.

ECG result will be interpreted by the Investigators and graded as:

- Normal
- Abnormal, not clinically significant OR
- Abnormal, clinically significant

Any abnormality in ECG observed, will be considered as an AE or SAE as appropriate.

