4.5.3. Potentially Clinically Important Vital Sign Values

Vital sign values are PCI if they meet both the observed value criteria and the change from baseline criteria. The PCI vital sign values are presented in Table 15 below:

Table 15: Potentially Clinically Important Vital Sign Criteria

Parameter	PCI Low	PCI High
Systolic blood pressure	≤90 mmHg and decrease ≥20 mmHg from baseline	≥180 mmHg and increase ≥20 mm Hg from baseline
Diastolic blood pressure	≤50 mmHg and decrease ≥15 mmHg from baseline	≥105 mmHg and increase ≥15 mmHg from baseline
Pulse rate	≤50 bpm and decrease ≥15 bpm from baseline	≥120 bpm and increase ≥15 bpm from baseline
Respiratory rate	≤8 brpm and decrease ≥7 brpm from baseline	≥25 brpm and increase ≥7 brpm from baseline
Temperature		≥38.3°C and increase ≥1.1°C from baseline

bpm=Beats per minute; brpm=Breaths per minute

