7.7.4. Vital Signs

For Day 180 Observational Population, vital signs (systolic and diastolic blood pressure, pulse rate, respiratory rate, body temperature and body weight) at specific visits and change from baseline at corresponding post baseline visits through Day 180 visit will be summarized using descriptive statistics by treatment arm (ie, CCH 1.68 mg, Placebo, and Overall) in double-blind studies (EN3835-302/303). The same set of tables will be reproduced for change from baseline considering Day 1 of the double-blind studies will also be presented.

For subjects in OLR Population after retreatment, vital signs (systolic and diastolic blood pressure, pulse rate, respiratory rate, body temperature and body weight) at specific visits and change from baseline at corresponding post baseline visits after Day 180 visits through end of treatment session assessments will be summarized by subject category (ie, Category I, II, and Overall) using descriptive statistics.

For Day 180 Observational Population, the Screening assessments done within 14 days of/ or Day 71/EOS visit in the double-blind studies will be used as baseline. For subjects in OLR Population after retreatment, the assessments at Screening B or unscheduled visits prior to/on the first dose date of retreatment in this study will be used as baseline.

The PCI vital signs values will be summarized by counts and percentages for Day 180 Observational Population and for subjects in OLR Population after retreatment, separately. Refer to [Table 15](#) for PCI criteria.

A subject listing will be presented for all vital signs parameters for Day 180 Observational Population and for subjects in OLR Population with retreatment separately.

7.7.5. 12-Lead ECG

The investigator interpretation of ECG results (normal, abnormal not clinically significant or abnormal clinically significant) at Screening B (for Category I and II retreated subjects) will be listed for OLR Population.

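### Table 17 and section 7.7.4 set different baselines for vital signs after retreatment, and Table 17 does not settle which applies to the Day 1 post-injection readings

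*SAP*

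**What the plan says.** The Table 17 row on the safety baseline after retreatment makes three statements that bear on vital signs:

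1. "For visits prior to/on first day of retreatment, Baseline is defined as the assessment values at Day 71/EOS visit in double-blind studies".
2. "For visits after first day of retreatment, baseline is defined as the last non-missing measurement/assessment prior to/on the first dose date of retreatment".
3. "For vital signs, the baseline will be the Day 1 pre-dose values". No visit restriction is attached.

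Section 7.7.4, for the Open Label Retreated (OLR) Population after retreatment, says "the assessments at Screening B or unscheduled visits prior to/on the first dose date of retreatment in this study will be used as baseline". It plans change-from-baseline summaries and PCI counts for that population, and it includes body weight among the vital signs.

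Section 3.11.3 schedules a reading before dosing on each treatment day and further readings "at 15 and 30 minutes after the last injection". Body temperature is taken before dosing and at 30 minutes only. Table 2 places Screening B at "Day -14 to -1 relative to Tx Visit 1". Section 4.5.3 states: "Vital sign values are PCI if they meet both the observed value criteria and the change from baseline criteria".

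**The concern.** Safety of retreatment is one of the primary objectives in section 2.1. The readings taken minutes after an injection are the most direct numerical data on acute effects, and most of what is tabulated from them is relative to baseline. If two sections name different baselines, two programmers can each follow the SAP and produce different change tables and different PCI counts. For the first session a third candidate, the double-blind Day 71/EOS value, is in play as well. Nothing in the SAP says which statement prevails.

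**Working it through.** No sample size or power figure is involved. The check sets the rules side by side, then applies the SAP's own PCI rule.

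**Which baseline each rule gives**

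| Reading | Table 17, opening sentence | Table 17, vital-signs sentence | Section 7.7.4 |
|---|---|---|---|
| Day 1, 15 and 30 min | Double-blind Day 71/EOS | Day 1 pre-dose | Screening B or unscheduled |
| Days 22, 43 and 71 | Not applicable | Day 1 pre-dose | Screening B or unscheduled |

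**Can section 7.7.4 be read to include Day 1 pre-dose?** No. Its date limit qualifies Screening B or unscheduled visits, and Treatment Visit 1 is a scheduled visit. The SAP names Day 1 when it means to include it. The after-retreatment baseline for CR-PCSS, PR-PCSS and PR-CIS in Table 17 reads "The assessments at Screening B/unscheduled assessment or Day 1 of the retreatment phase prior to/on the first dose date of retreatment". The section 7.7.4 wording matches the laboratory baseline in section 7.7.3. It fits there because Table 2 schedules laboratory tests at Screening B and none on Day 1. Vital signs are scheduled on Day 1.

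**How many readings are affected?** For a subject who attends all three sessions and Day 71, blood pressure, pulse and respiratory rate have 2 (Day 1) + 3 (Day 22) + 3 (Day 43) + 1 (Day 71) = 9 reading times after the first injection. The conflict between Table 17 and section 7.7.4 covers all 9. The ambiguity inside Table 17 covers the 2 on Day 1. For temperature the counts are 1 + 2 + 2 + 1 = 6, and 1.

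**Does the baseline change a flag?** Table 15 makes a systolic value PCI-low if it is ≤90 mmHg and has fallen by ≥20 mmHg. For a reading v ≤ 90, the flag is set when baseline ≥ v + 20. Two candidate baselines disagree whenever v + 20 is above the lower one and not above the higher one. The values below are assumed, for illustration only.

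- Case A, v = 88, so the baseline must be at least 108. Screening B 112: fall 112 − 88 = 24, flagged. Day 1 pre-dose 104: fall 104 − 88 = 16, not flagged. A double-blind Day 71 value of 124 gives 124 − 88 = 36, flagged.
- Case B, v = 90, so the baseline must be at least 110. Screening B 106: fall 106 − 90 = 16, not flagged. Day 1 pre-dose 118: fall 118 − 90 = 28, flagged. A double-blind Day 71 value of 104 gives 104 − 90 = 14, not flagged.

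The discrepancy can go in either direction.

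**How far apart are the candidate baselines in time?** Screening B and Day 1 pre-dose are 1 to 14 days apart. The double-blind value is about 6 months old at the earliest retreatment. The SAP's example of retreatment starting on Day 351 makes it about 11.5 months (351 ÷ 30.4). A footnote to Table 3 gives an outer limit of about 36 months, although the same footnote describes ending the trial at Day 1080, so the upper end may not occur.

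**Body weight.** Section 7.7.4 summarises weight with the vital signs, but Table 2 schedules it at Screening B and Days 22, 43 and 71, not on Day 1. The Day 1 pre-dose rule therefore has no scheduled weight to use.

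**The case against.** The best defence is that Table 17 answers the question itself. Its sentence on vital signs is specific and has no visit limit, so under the usual preference for the specific over the general it governs every post-injection reading, including those on Day 1. Section 7.7.4 may simply have inherited the laboratory wording.

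Two stronger readings are tempting, and this defence disposes of both:

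- A reader might infer that Table 17, taken literally, compares the first session's post-injection readings with a double-blind value months or years old. That is one possible reading, if the vital-signs sentence only elaborates the rule for later visits. It is not the only one, and section 7.7.4 would not use the double-blind value for these readings either.
- A reader might infer that a 30-minute post-injection reading could itself become the baseline, because the general rule admits values on the first dose date. For vital signs that requires setting aside the sentence that says pre-dose.

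On impact, the PCI counts are descriptive and no hypothesis test depends on them. All vital signs of retreated subjects are listed, and section 3.11.3 treats observed abnormalities as adverse events whatever the baseline. That stands: an acute reaction would not vanish from the report.

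The conflict between Table 17 and section 7.7.4 also stands. The SAP gives no order of precedence, and the specific-over-general argument does not help between two statements that are both specific to vital signs.

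**Conclusion.** The SAP contradicts itself on the vital-sign baseline after retreatment: Day 1 pre-dose in Table 17, Screening B or unscheduled visits in section 7.7.4, for the same tables. Separately, Table 17 is ambiguous for the Day 1 readings at 15 and 30 minutes, where its opening sentence and its vital-signs sentence give different baselines. Both conclusions rest on the text alone.

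The practical size is a change in change-from-baseline summaries and PCI counts. How many subjects would be affected cannot be estimated from the document, and the worked cases use assumed values. The point should be fixed because the affected displays serve a primary safety objective and cannot be reproduced uniquely as written. It does not threaten the trial's conclusions.

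**What to change.** State one rule and use it in both Table 17 and section 7.7.4:

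- For every vital-sign reading after the first retreatment injection, including Day 1 at 15 and 30 minutes, baseline is the last value before that injection: Day 1 pre-dose or, if that is missing, the latest Screening B or unscheduled value.
- Limit the double-blind Day 71/EOS baseline to readings taken before the first retreatment injection. The Day 1 pre-dose reading then keeps a comparator.
- Where the rules admit a value taken up to and including the first dose date, require it to be taken before the first injection. This rules out any post-injection value as baseline.
- For body weight, use the last weight before the first injection, which is the Screening B weight, because none is scheduled on Day 1.

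The cost is SAP wording and the matching derivation specification. No new data or visits are needed.
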